3.1. Staging Laparoscopy

3.1.1. Patients who meet eligibility criteria will be taken to the operating room for staging laparoscopy and peritoneal washings. At laparoscopy biopsies of the peritoneum will be done and used later to confirm status of peritoneal disease (not as a part of the staging procedure but as part of the study).

- Any suspicious lesions that might preclude resection to NED will be biopsied as well.
- Liver ultrasound to confirm axial imaging findings will be done.
- Randomization and stratification will be done after laparoscopy and only after the results of the peritoneal washings are known (within one week of laparoscopy).

3.1.2. Patients will then be randomized to receive gastrectomy and/or metastasectomy plus systemic therapy (GYMS arm) or systemic therapy alone (SA arm).

- Patients randomized to receive the standard of care (SA arm) will receive systemic therapy (as described in Section 3.5). **Note:** Patients may undergo palliative gastrectomy if indicated but must begin chemotherapy within 6 weeks of gastrectomy (8 weeks following randomization).
- Patients randomized to receive gastrectomy and/or metastasectomy plus systemic therapy (GYMS arm) will be taken to the operating room within 1-2 weeks of randomization (as soon as feasible). Patients may undergo surgery only at the NCI. Subsequently, patients will receive systemic therapy within 4 to 16 weeks after surgery and/or when fully recovered from surgery. Patients who do not recover within 16 weeks will be taken off treatment and followed for survival. (**Note:** patients who undergo thoracotomy for pulmonary metastases must be able to receive systemic therapy within 24 weeks of their initial surgery.) This is an intent-to-treat phase III trial.

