3.5. Systemic Chemotherapy Therapy

3.5.1. Guidelines

Patients who randomize to receive systemic chemotherapy alone (SA) will begin treatment within 14 days of randomization; patients who undergo palliative gastrectomy will begin chemotherapy within 6-8 weeks of randomization. Patients who randomize to surgery plus chemotherapy (GYMS) will begin treatment approximately 6-8 weeks following surgery (24 weeks for patients requiring sequential thoracic and abdominal surgery). **Note:** patients must meet eligibility requirements prior to beginning chemotherapy. Patients who do not recover from the surgical procedure within the stated timeframe will be removed from treatment and followed for survival.

Systemic therapy may be administered by the patient's local oncologist in collaboration with the PI or at the NCI by the Medical Oncology Branch. Systemic therapy will follow the guidelines for the FOLFOXIRI regimen⁷⁷. Chemotherapy and supportive care will be administered in accordance with each institution's policies for the administration of chemotherapeutic agents.

During treatment, the treating oncologist will be asked to fax the following information (Appendix 8) to the research nurse (noted below) at the conclusion of every other cycle (4 weeks):

- chemotherapy administration sheets including dose reductions and reason for dose reduction
- laboratory test results
- other clinically relevant information

The patient will be asked to maintain a diary to be faxed to the research nurse every 4 weeks:

[name] RN
[contact]

All systemic chemotherapy will be administered based on actual body weight if within 20% above or below the ideal body weight. If actual weight is not within 20% of ideal body weight, then ideal body weight will be used to calculate systemic chemotherapy doses.

Ideal body weight will be calculated based upon the following formula:

$$\begin{aligned} \text{IBW (male, in kg)} &= \{(\text{Height in inches} - 60 \} \times 2.3 \} + 50 \\ \text{IBW (female, in kg)} &= \{(\text{Height in inches} - 60 \} \times 2.3 \} + 45.5 \end{aligned}$$

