3.10. Off Study Criteria

- Death

- Unwillingness to participate in study specified follow up (including phone contact)
- If the physician deems it is no longer in the best interest of the patient to remain on study

Note: As the objective of this study is overall survival, every attempt will be made to follow patients for life.

Patients will be officially taken off study by contacting the CRO.

3.11.Measurement of Health Related Quality of Life

Baseline Quality of Life Questionnaires (QOL) will be completed prior to randomization, prior to cycle 9 of chemotherapy and then every 12 weeks (+/- 2 weeks) for the first 2 years, every 6 months for the next 3 years, and yearly thereafter. (Note: patients who begin chemotherapy >5 weeks following randomization will be asked to complete the QOL prior to the first cycle of chemotherapy.

Patients will be informed of the details of the QOL part of this study and reassured that their decision to participate will not affect their participation in the either of the treatment arms of this protocol. Once enrolled, the patient has the right at any time to elect not to continue completing the questionnaires. In the event a patient goes off study prior to completion of the follow up time points, the data gathered from their completed QOL questionnaires will be included in the final analysis.

To QOL parameters and quality of life adjusted survival between the two study groups, we will use tools specifically developed for assessment of QOL in gastric cancer patients: FACT-Ga, ; Blazeby JM, Eur J cancer 2004 (Appendix 6). Measures will be initially administered by the Associate Investigator Research Nurse or designee prior to randomization. The Research Nurse will assess the patient's ability to read, and if the patient is unable to read, it will not be administered. The Research Nurse or designee will administer the questionnaires providing a firm surface at a table or a clipboard and a pencil. The patients will be directed to complete the questionnaires using the following instructions:

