We would like to better understand how you and other persons in this study feel, how well you are able to do your usual activities, and how you rate your health while you are participating in this research study. To help us better understand these things about you and other persons participating in this study, please complete these two questionnaires about your quality of life. Both questionnaires should not take longer than 15 minutes to complete.

The questionnaires are simple to fill out. Be sure to read the instructions on the top of each questionnaire. Remember, this is not a test and there are no right or wrong answers. Choose the response that best represents the way you feel. I will quickly review the questionnaires when you are done to make sure that all the items have been completed. Please answer all the items with the response that is most applicable.

You should answer these questions by yourself. Your husband/wife or other family members or friends should NOT assist you in completing the questionnaires. Please fill out the questionnaires now. Return the questionnaires to me when you have completed them. We will be asking you to complete these again during some of your follow up visits. If you have any questions, please ask.

Once the patient has completed the questionnaires, the Research Nurse or designee, will review them for completeness and thank the patient for their cooperation. Subsequent measurements will be administered by the Associate Investigator Research Nurse, or designee, when the patient returns for follow-up visits as specified in section 3.9.

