The Research Nurse or designee will request that the patient complete the questionnaires prior to seeing the physician, as the interaction between the patient and physician may influence the patient's answers to the questionnaires. In the event a patient is taken off study, patients will be asked to complete one last set of questionnaires (as appropriate to the point of withdrawal) and the data will be included in the analysis. Patients who are only being followed for length of survival will be asked to continue to participate in completing the measures at the set intervals (every 6-12 months) through the mail. Patients will be phoned prior to the scheduled date of measurement and asked to complete the questionnaire; the FACT-Ga will then be mailed to the patient with a self-addressed return envelope and a cover letter with the script above as directions. If the questionnaires are not returned within 2 weeks, patients are phoned again.

4. Supportive Care:

During the post-operative period patients will receive all standard of care supportive measures including nasogastric tube drainage and bowel rest for ileus, pulmonary toilet teaching and incentive spirometry to prevent atelectasis, transfusions, and antibiotics as indicated.

During the administration of systemic chemotherapy patients will receive all necessary supportive care as per the guidelines of the treating physician and institution. This may include:

- Blood transfusions and growth factor support as necessary for the management of myelosuppression. Filgrastim 5 mcg/kg/day subcutaneously may be administered for ANC less than 1000 mm³ or as per the guidelines of the treating institution. **Note:** Filgrastim will not be administered prophylactically during systemic chemotherapy.
- Neutropenic fever will be treated with broad-spectrum antibiotics pending culture results.
- Renal dysfunction (very rare) from oxaliplatin will be managed with supportive measures such as avoidance of renal toxic drugs, maintenance of good renal perfusion (hydration), and diuretics as necessary.
- Diarrhea will be managed with medication such as diphenoxylate/atropine or loperamide.

- Mucositis will be treated with bicarbonate rinses or anesthetic mouth wash.
- Premedication with antiemetics, including 5-HT3 blockers with or without dexamethasone, is recommended during systemic chemotherapy.

5. **Data Collection and Evaluation:**

5.1. **Data Collection**

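### Section 3.11 gives survival-only patients, by its written routes almost all surgical-arm non-recoveries, sparser quality-of-life forms, and names only the FACT-Ga for mailing

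*Combined protocol and SAP*

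**What the plan says.** **Standard schedule.** Section 3.11 asks for QOL forms before randomization, before cycle 9, and then "every 12 weeks (+/- 2 weeks) for the first 2 years, every 6 months for the next 3 years, and yearly thereafter". One form is added: "patients who begin chemotherapy >5 weeks following randomization will be asked to complete the QOL prior to the first cycle of chemotherapy".

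**Survival-only schedule.** The same section says: "Patients who are only being followed for length of survival will be asked to continue to participate", by "completing the measures at the set intervals (every 6-12 months) through the mail". Patients are phoned first, then "the FACT-Ga will then be mailed to the patient", with a second call if nothing comes back in two weeks.

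**Routes to survival-only follow-up.** Section 3.1.2 says of the GYMS arm: "Patients who do not recover within 16 weeks will be taken off treatment and followed for survival". Section 3.5.1 says that patients who do not recover from the operation in the time allowed "will be removed from treatment and followed for survival". That sentence follows text on both arms, so it could also reach a patient on systemic therapy alone (SA) who had a palliative gastrectomy.

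**Instruments.** The QOL objective in section 1.1.2 names three: the FACT-Ga and two EORTC tools. The patient script in section 3.11 says "please complete these two questionnaires about your quality of life". The mailing text names one.

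**Analysis.** Section 5.4 compares the arms at individual time points and on change from baseline, probably by Wilcoxon rank sum tests, unadjusted and as a secondary evaluation. It gives no rule for missing forms.

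**The concern.** Every patient treated as assigned in the GYMS arm has a major operation. In the SA arm only those who need a palliative gastrectomy do. A reduced schedule that starts when a patient fails to recover from surgery therefore applies almost only to GYMS, and to patients whose QOL is likely to be poor. A time-point comparison of available forms would then under-represent poor surgical recoveries in one arm.

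At stake is the QOL comparison, where the burden of surgery on patients should become visible. If the thinning acts as expected, it makes GYMS look better than it is. For the EORTC tools, results after baseline would describe only patients still assessed in clinic.

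**Working it through.** **1. The plan's own figures.** The plan gives no sample size or power for QOL. Its survival inputs reproduce. Medians of 12 and 20 months give a hazard ratio of 20/12 = 1.667, and 4 × (1.960 + 0.842)² / (ln 1.667)² rounds up to the stated 121 deaths. Twelve-month survival is 50% in SA and 0.5^(12/20) = 66% in GYMS, as section 5.4 states. With 68 per arm, about 34 SA and 45 GYMS patients are expected alive at 12 months.

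**2. Scheduled forms over two years (104 weeks), clock from randomization.**
- Standard: 104/12, so 8 complete intervals and 8 forms.
- Survival-only: 4 forms if 6-monthly, 2 if 12-monthly.
- Reduction: 1 − 4/8 = 50% to 1 − 2/8 = 75%.

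Section 3 (study design) dates follow-up evaluations from randomization. Section 3.9, to which section 3.11 refers for follow-up visits, counts from the end of chemotherapy. On that clock an SA patient who starts by week 2 and has 12 two-week cycles finishes near week 26, leaving (104 − 26)/12 = 6 complete intervals. So 8 is a maximum.

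**3. First form after baseline for a patient who does not recover.** The patient never starts chemotherapy, so neither the cycle 1 nor the cycle 9 form falls due. The closing set of questionnaires in section 3.11 is for patients taken off study. These patients are taken off treatment only. If the mail interval runs from the switch (the documents do not say), then with surgery 1-2 weeks after randomization, the 16-week limit of section 3.1.2, and 52/12 = 4.33 weeks per month:
- earliest: (1 + 16)/4.33 + 6 = 9.9 months;
- latest: (2 + 16)/4.33 + 12 = 16.2 months.

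That is about 10-16 months after randomization. Section 3.5.1 gives about 6-8 weeks after surgery as the time for starting chemotherapy and ties removal to its stated timeframe. On that basis the range is (1 + 6)/4.33 + 6 = 7.6 to (2 + 8)/4.33 + 12 = 14.3 months. The two sections need reconciling.

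**4. Size of the bias.** The documents give neither a non-recovery rate nor a QOL deficit. I assume a fraction f of 5-20% of GYMS (0.05 × 68 = 3.4 to 0.20 × 68 = 13.6 patients), all absent from a given time point.
- If they score 0.5-1.0 SD below the rest, the GYMS mean rises by f × deficit, from 0.05 × 0.5 = 0.025 SD to 0.20 × 1.0 = 0.20 SD.
- If they are exactly the lowest scorers, the rise is φ(z)/(1 − f), with z the f-quantile of the standard normal: 0.11, 0.19, 0.27 and 0.35 SD at f = 5, 10, 15 and 20%.

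Simulated two-sided Wilcoxon tests at 0.05 with no true difference reject as follows:

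| Scenario | f = 5% | 10% | 15% | 20% |
|---|---|---|---|---|
| 60 per arm, correlation 1 | 8% | 16% | 28% | 40% |
| 60 per arm, correlation 0.5 | 6% | 8% | 11% | 13% |
| 45 GYMS, 34 SA, correlation 0.5 | 5.7% | 6.4% | 8.1% | 10.7% |
| 60 per arm, correlation 0.5, SA loses half as many | 5.2% | 6.0% | 7.0% | 8.4% |

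The correlation is between non-recovery and QOL. The last three rows span about 5-13%. At 60 per arm, correlation 0.5 and f of 10-20%, some 88-99% of the false positives favour GYMS.

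**The case against.** **These patients are not lost.** A reader might infer that the comparison drops them. They have a baseline form, are asked to continue, are phoned before each mailing and again if needed, and can still return the FACT-Ga. This stands: the FACT-Ga is thinned, not removed.

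**The SA arm is not complete either.** A reader might assume that SA is represented by everyone. SA patients also die, progress, stop for toxicity or cannot return. Section 3.9 moves patients in both arms who cannot return to phone contact, and QOL is not in its list of information to obtain. This stands, and SA loss of that kind would offset part of the bias.

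**The wording is ambiguous.** Section 3.11 does not define survival-only follow-up by reference to sections 3.1.2 or 3.5.1; the link is an inference from matching language. The 6-12 month interval also resembles the later part of the standard schedule. The mailing paragraph speaks of measures and questionnaires in the plural and encloses the script, which mentions two forms. So the text does not prove that EORTC forms stop, only that none is named for mailing. Against this, a patient who fails the 16-week limit enters survival-only follow-up during the 12-weekly phase, and no 12-week mailing is provided.

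**The mail interval does not cause the earliest gap.** This also stands. The cycle-anchored forms are missed whatever the mail interval, and the pre-cycle-1 form has almost no SA counterpart because SA chemotherapy starts within 14 days unless there is a palliative gastrectomy. It changes the remedy: altering the mail interval alone would not be enough.

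**Conclusion.** The point holds for a secondary endpoint. As written, the plan creates QOL missingness related to arm and outcome, through a sparser schedule whose only explicit entry routes are failures of surgical recovery and through early forms tied to chemotherapy that these patients never start. The likely direction favours GYMS.

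The size is uncertain. Under 5-20% non-recovery and a correlation of 0.5, both assumptions, the false-positive rate is about 5-13%, close to nominal at the low end. The 8-40% range is an upper bound: it needs complete loss, perfect correlation, no informative SA loss and 60 responders per arm, more than the design expects alive at 12 months. It should not be read as the expected error rate.

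The instrument mismatch (three, two, one) needs no assumption. Overall survival, the primary endpoint, is not touched.

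**What to change.** - In section 3.11, give survival-only patients in both arms the same QOL time points as all other patients, by mail or phone.
- Date all QOL forms from randomization, not from chemotherapy cycles or the end of chemotherapy, and align section 3.9 with the study-design statement in section 3.
- Mail every instrument in the QOL objective. Use one instrument list in section 1.1.2, section 3.11, the patient script and the mailing text.
- Say in section 3.11 which patients count as followed only for survival. In section 5.4, state how missing forms and deaths are handled, and report completion by arm and reason.

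**Cost.** Wording changes, and a few extra mailings and calls per survival-only patient through the procedure already planned. There is some added burden on ill patients, who may decline. Sample size and treatment rules do not change. Early QOL forms not collected on time cannot be recovered later.

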1.1. Study Objectives

1.1.1. Primary Objective:

- To determine whether a therapeutic approach that includes gastrectomy and/or metastasectomy plus systemic therapy is superior to the standard of care approach that includes systemic therapy alone in terms of overall survival for patients who present with limited metastatic gastric cancer (MGC).

1.1.2. Secondary Objectives:

- To compare progression-free survival (PFS) between the two study arms
- To analyze prognostic factors and generate potential selection criteria for patients who present with limited gastric cancer metastases that might benefit from gastrectomy and/or metastasectomy plus systemic therapy.
- To analyze prognostic factors and generate potential selection criteria for patients who present with limited gastric cancer metastases that will not benefit from gastrectomy and/or metastasectomy.
- To determine if surgical resection impacts the dosing and duration of subsequent chemotherapy administration
- To compare quality of life (QOL) parameters between the two study groups. We will use tools specifically developed for assessment of QOL in gastric cancer patients: FACT-Ga, EORTC QLQ-STO22 and the SROTC QLQ-C30¹⁻⁴.
- To determine and compare patterns of disease recurrence between the two therapeutic approaches and their clinical implications.

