Note: Patients at risk for splenectomy (proximal T3-T4 lesions) may receive triple vaccination (Pneumococcal, Meningococcal, *Haemophilus influenzae*) prior to surgery.

3.2.5. Hepatic metastasectomy:

- Intraoperative ultrasound will be performed on all patients to detect disease not witnessed on preoperative imaging. Unexpected findings will be recorded in the patients chart.
- The goal of hepatic metastasectomy is to render the patient NED with at least 1 cm negative margins when possible.
- The preferred modality of hepatic metastasectomy is anatomical segmental resection. For single lesions, when possible, segmentectomy should be performed. For more than a single isolated lesion, a sectorectomy or partial hepatectomy should be performed if feasible. In all cases, the surgeon should strive to obtain negative margins.

- A non-anatomic wedge resection shall be performed only for small superficial lesions deemed resectable to negative margins by intra-operative ultrasound and preoperative imaging.
- In selected cases, intraoperative RFA and/or microwave ablation may be used at the discretion of the operating surgeons if deemed in the best interests of the patient.
- Portal vein ligation/embolization should be considered in selected patients to preserve post-operative liver function.
- A formal hepatic lobectomy will be done for large lesions spanning more than two sectors, or multiple lesions within a single hepatic lobe.
- In all cases of hepatic gastric metastasis undergoing liver resection, the surgeon should perform portal and hepatic artery lymph node dissection whenever possible.

3.2.6. Peritoneal metastasectomy (cytoreductive surgery):

- If there is evidence that the extent of disease is beyond the ability to be debulked such that the largest residual tumor nodule is less than or equal to 0.5 cm, patients will be considered ineligible and removed from treatment.
- For patients with primary peritoneal metastases (small disease load; P0-P2 disease) without massive ascites or intestinal obstruction, all visible disease will be resected if technically feasible.
- Complete peritonectomy for patients with peritoneal disease includes the following: the right and left sub-diaphragmatic peritoneum, the falciform ligament, lesser and large omentum, anterior, right and left abdominal wall down to the paracolic gutters and the pelvic peritoneum.

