Data will be collected using the NCI C3D web based data collection system. Quality of life will be assessed using questionnaires as specified in section 3.11.

5.2. **Response Criteria**

5.2.1. **Surgery + chemotherapy arm**

Because of the nature of peritoneal imaging and because cytoreductive surgery will likely eliminate all imageable disease, response can only be measured in terms of radiographic or symptomatic disease-free survival and overall survival. Patients will be followed with CT scans at predetermined intervals as described in Section 3.9. At any time point when there is evidence of progressive disease (imageable tumor nodules or increasing ascites persistent on CT scans as interpreted by the official interpretation of the imaging studies) the patients will be scored as progressive disease. In some cases this may require successive scans, but the time of recurrence will be retrospectively defined at the point the first scan demonstrated imageable disease. Patients who have symptoms of peritoneal tumor recurrence will be followed closely with serial scans and where necessary, laparoscopy (GYMS arm) in order to confirm disease status.

5.2.2. **Systemic chemotherapy alone arm**

Lesions will be evaluated using the RECIST criteria as described below.

Evaluation of target lesions*

- Complete Response (CR): Disappearance of all target lesions
- Partial Response (PR): At least a 30% decrease in the sum of the longest diameter (LD) of target lesions taking as reference the baseline sum LD.
- Progression (PD): At least a 20% increase in the sum of LD of target lesions taking as reference the smallest sum LD recorded since the treatment started or the appearance of one or more new lesions.
- Stable Disease (SD): Neither sufficient shrinkage to qualify for PR nor sufficient increase to qualify for PD taking as references the smallest sum LD.

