* All measurable lesions up to a maximum of 10 lesions representative of all involved organs should be identified as **target lesions** and recorded and measured at baseline. Target lesions should be selected on the basis of their size (lesions with the longest diameter) and their suitability for accurate repetitive measurements (either by imaging techniques or clinically). A sum of the longest diameter (LD) for all target lesions will be calculated and reported as the baseline sum LD. The baseline sum LD will be used as reference to further characterize the objective tumor response of the measurable dimension of the disease.

Evaluation of non-target lesions**

- Complete Response (CR): Disappearance of all non-target lesions and normalization of tumor marker level.
- Non-Complete Response: Persistence of one or more non-target lesions
- Progression (PD): Appearance of one or more new lesions. Unequivocal progression of existing non-target lesions

** All other lesions (or sites of disease) should be identified as **non-target lesions** and should also be recorded at baseline. Measurements are not required, and these lesions should be followed as “present” or “absent.”

Evaluation of best overall response

The best overall response is the best response recorded from the start of the treatment until disease progression/recurrence (taking as reference for progressive disease the smallest measurements recorded since the treatment started). The patient's best response assignment will depend on the achievement of both measurement and confirmation criteria.

Target Lesions	Non-Target Lesions	New Lesions	Overall Response
CR	CR	No	CR
CR	Non-CR/Non-PD	No	PR
PR	Non-PD	No	PR
SD	Non-PD	No	SD
PD	Any	Yes or No	PD
Any	PD	Yes or No	PD
Any	Any	Yes	PD

Confirmatory Measurement/Duration of Response Confirmation

To be assigned a status of PR or CR, changes in tumor measurements must be confirmed by repeat studies that should be performed at least 4 weeks after the criteria for response are first met. In the case of SD, follow-up measurements must have met the SD criteria at least once after study entry at a minimum interval of 6-8 weeks.

Duration of Overall Response

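### The two arms compared by the PFS log-rank test are scored for progression by different rules, and the cycle-9 quality-of-life form falls at different weeks in each arm

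*Combined protocol and SAP*

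**What the plan says.** **PFS.** Section 1.1.2 lists as a secondary objective "To compare progression-free survival (PFS) between the two study arms". Section 5.4 does this with Kaplan-Meier curves and a two-tailed log-rank test. It does not say whether death or clinical progression is an event, or when a patient is censored.

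Section 5.2 then splits by arm.

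- **GYMS (5.2.1).** The premise is that surgery will probably clear visible disease, so "response can only be measured in terms of radiographic or symptomatic disease-free survival and overall survival". The scoring rule starts "At any time point when there is evidence of progressive disease (imageable tumor nodules or increasing ascites persistent on CT scans", and continues "as interpreted by the official interpretation of the imaging studies". Recurrence is backdated to the first scan that showed disease. Patients with symptoms are followed by serial scans and, "where necessary, laparoscopy (GYMS arm) in order to confirm disease status".
- **SA (5.2.2).** "Lesions will be evaluated using the RECIST criteria as described below": at least 20% growth in the sum of longest diameters over the smallest recorded value, a new lesion, or "Unequivocal progression of existing non-target lesions". No backdating rule is given.

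Section 3.7 calls for RECIST without distinguishing arms. The design list that opens section 3 gives the measurement of progression to a radiologist blinded to arm. Section 3.9 sets a CT around randomisation as the baseline for progression in both arms.

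**Quality of life.** Section 3.11 schedules forms before randomisation, before chemotherapy cycle 9, and every 12 weeks thereafter. Patients starting chemotherapy more than 5 weeks after randomisation complete an extra form before cycle 1. Section 5.4 compares the arms at individual time points and on change from baseline.

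**The concern.** A log-rank comparison needs the same event in both arms. Here the rule depends on the assigned arm, so part of any PFS difference could come from the definition and not from the treatment. The plan also has three unreconciled statements: RECIST for everyone (3.7) against an arm-specific rule (5.2.1), the blinded radiologist (section 3) against the official imaging report (5.2.1), and a baseline CT (3.9) that in GYMS precedes the operation that removes the lesions.

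The quality-of-life problem is similar. Cycle 9 is a point in chemotherapy, and chemotherapy starts weeks later in GYMS because surgery comes first. A comparison labelled as one time point would compare patients at different times since randomisation, and only those still on chemotherapy.

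**Working it through.** The plan states no figure for PFS or quality of life. Its overall-survival design is not touched, and it reproduces: 4 × (1.960 + 0.842)² / (ln(20/12))² = 31.4 / 0.261 = 120.3, rounded up to the stated 121 deaths.

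**PFS: the rules side by side**

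| Situation | GYMS (5.2.1) | SA (5.2.2) | Same? |
|---|---|---|---|
| New lesion after complete resection, or new lesion in SA | Progression | Progression | Yes |
| Increasing ascites | Progression if persistent on CT | Not named; could enter as non-target progression | May overlap |
| Symptoms | Named in the endpoint description | Not listed as an event | No |
| Laparoscopy | Available to confirm status | Not mentioned | No |
| Date of event | Backdated to first scan showing disease | No backdating rule | No |
| Unresected nodule | No growth criterion stated | 20% growth in the sum, or unequivocal non-target progression | Depends on reading |

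Clinical progression also ends treatment in both arms (3.8), but no section says whether it is a PFS event.

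The last row can arise in two ways. Under 3.2.6, if disease cannot be debulked, "patients will be considered ineligible and removed from treatment", although 3.1.2 calls the trial intent-to-treat. Under 3.2.8, lung resection may be delayed by up to 16 weeks in synchronous disease.

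Patients who do not recover from surgery in time are followed for survival (3.1.2, 3.5.1). The scans in 3.7 are tied to chemotherapy, and 3.9 counts from its completion. For patients who never start chemotherapy, the plan gives neither a clear progression-scan schedule nor a censoring rule.

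**Quality of life: week of the cycle-9 form**

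Inputs: SA starts chemotherapy within 14 days of randomisation (2.3, 3.5.1). GYMS surgery is 1-2 weeks after randomisation (3.1.2). GYMS chemotherapy follows surgery by about 6-8 weeks (3.5.1) or 4-16 weeks (3.1.2). Cycles last 14 days, 12 cycles planned (3.5.2).

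Cycle 9 begins 8 × 2 = 16 weeks after cycle 1. Weeks from randomisation:

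| Group | Chemotherapy start | Cycle-9 form |
|---|---|---|
| SA | 0-2 | 16-18 |
| GYMS, 3.5.1 | (1+6) to (2+8) = 7-10 | 23-26 |
| GYMS, 3.1.2 | (1+4) to (2+16) = 5-18 | 21-34 |

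The SA and GYMS ranges do not overlap. The smallest gap is 21 − 18 = 3 weeks and the largest is 34 − 16 = 18 weeks. Two subgroups lie outside the table. SA patients with palliative gastrectomy start at weeks 6-8 (3.5.1), so their form falls at weeks 22-24. GYMS patients with staged lung surgery may start as late as week 24 from randomisation (3.2.8), putting the form at week 40, or 24 weeks after surgery (3.5.1), which is 2 + 24 + 16 = week 42.

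The extra pre-cycle-1 form goes mostly to GYMS and does not move the cycle-9 form.

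**Later forms: three readings**

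- Clock from randomisation (section 3): matched by week.
- 12 weeks after completing chemotherapy (3.9), that is start + 24 + 12: SA weeks 36-38; GYMS 43-46 or 41-54. SA responders who continue past 12 cycles are later still.
- 12 weeks after the cycle-9 form (3.11 read directly): SA weeks 28-30; GYMS 35-38 or 33-46.

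**The case against.** The strongest defence is that 5.2.1 was written for patients with no visible disease after surgery. It asks for evidence of progressive disease and speaks of recurrence, and 3.9 sets a baseline CT for both arms. Against that baseline an unchanged nodule has not progressed. This stands in part. A reader might infer that the plan counts any stable unresected nodule in GYMS as progression; the text permits that reading but does not require it. What remains is that 5.2.1 asks for an increase only for ascites, and itself says only that surgery will likely clear the disease.

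A reader might also infer a measurable PFS bias against GYMS, by supposing that some share of patients with unresected disease is scored as progressed on the pre-chemotherapy CT. The documents do not support this. Patients who cannot be debulked are removed from treatment, so on the natural reading they have no pre-chemotherapy CT. Staged-lung patients would normally have that CT after the resection. No share is given, and eligibility requires disease judged resectable, with laparoscopy before randomisation.

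The blinded radiologist reduces reader bias but does not make two criteria equal, and 5.2.1 points to a different reading.

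For quality of life, tying a form to a stage of treatment is a legitimate choice, and section 5.4 leaves the tests tentative, so analysis by actual date is open. That is fair, but the plan does not say it will be done. Mailed and off-study forms (3.11) help somewhat without being at matched weeks. Section 3 and 3.9 need not contradict each other outright: 3.9 may say when the follow-up phase begins and section 3 which clock its visits use. The plan should say so.

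**Conclusion.** The point holds for two secondary endpoints. PFS has an arm-dependent progression rule, no stated event definition and no censoring rule. The rules agree on new lesions after complete resection and can differ on ascites, symptoms, laparoscopic findings, dating and unresected disease. The size and direction of the effect on PFS cannot be determined from the documents, so no hazard ratio or false-positive rate should be attached to it.

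The quality-of-life offset can be stated: weeks 16-18 in SA against 23-26 or 21-34 in GYMS at cycle 9. This assumes on-schedule cycles, no palliative gastrectomy and no staged lung surgery. It shows different timing and a form limited to patients still on chemotherapy; its effect on scores cannot be sized. Later forms are matched or offset depending on which section governs.

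It would be wrong to carry this over to the primary analysis: overall survival does not depend on progression scoring or on these forms. The change should be made, but the trial's main conclusion does not rest on it.

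**What to change.** 1. Define PFS once for both arms: randomisation to first RECIST progression (including a new lesion) or death. Use the same handling of ascites, symptoms and laparoscopy, the same dating and the same censoring, read by the blinded radiologist already named. Only the reference scan differs: the first post-operative scan in GYMS, where a lesion absent at baseline counts as new, and the baseline scan in SA. State that unresected disease counts on growth, not on presence.
2. Time quality-of-life forms from randomisation in both arms. Where forms are already collected, analyse by actual time from randomisation. Reconcile section 3, 3.9 and 3.11 on the follow-up clock.
3. For patients who never start chemotherapy, state a progression-censoring rule and a sensitivity analysis. No added scans are required.
4. The sponsor must reconcile the GYMS chemotherapy-start windows in 3.1.2, 3.2.8 and 3.5.1.

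The cost is protocol and SAP wording, reading existing scans under one rule, and some quality-of-life forms that no longer coincide with chemotherapy visits. Weeks at which no form was collected cannot be recovered.
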